9.2. Definition of Serious Adverse Event

If an event is not an AE per the definition above, then it cannot be an SAE even if serious conditions are met (eg, hospitalization for signs/symptoms of the disease under study, death due to progression of disease).

A serious adverse event is defined as any untoward medical occurrence that, at any dose:

a. Results in death

b. Is life-threatening

The term "life-threatening" in the definition of "serious" refers to an adverse drug experience that places the participant, in the opinion of the initial reporter, at immediate risk of death from the adverse experience as it occurs. This does not include an adverse drug experience that, had it occurred in a more severe form, might have caused death.

c. Requires inpatient hospitalization or prolongation of existing hospitalization

In general, hospitalization signifies that the participant has been detained (involving at least an overnight stay) at the hospital or emergency department for observation and/or treatment that would not have been appropriate in the physician's office or outpatient setting. Complications that occur during hospitalization are AEs. If a complication prolongs hospitalization or fulfills any other serious criteria, the event is serious. When in doubt as to whether hospitalization occurred or was necessary, the AE should be considered serious.

Hospitalization for elective treatment or planned surgery (eg, stent replacement, hip surgery) is not considered an SAE.

Hospitalization for medical interventions in which no unfavorable medical occurrence occurred (ie, elective procedures or routine medical visits) is not considered an SAE.

d. Results in persistent or significant disability/incapacity

• The term "disability" means a substantial disruption of a person's ability to conduct normal life functions. This definition is not intended to include experiences of relatively minor medical significance, such as uncomplicated headache, nausea, vomiting, diarrhea, influenza, and accidental trauma (eg, sprained ankle), that may interfere with or prevent everyday life functions but do not constitute a substantial disruption.

e. Is a congenital anomaly/birth defect

f. Is an important medical event

An important medical event is an event that may not result in death, be immediately life-threatening, or require hospitalization but may be considered serious when, based on appropriate medical judgment, the event may jeopardize the participant and may require medical or surgical intervention to prevent one of the outcomes listed in the above definition. Examples of such events include new invasive or malignant cancers; intensive treatment in an emergency department or at home for allergic bronchospasm, blood dyscrasias, or convulsions that do not result in hospitalization; or development of drug dependency or drug abuse. Secondary malignancies should always be considered SAEs.

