9.1. Definition of Adverse Event

Adverse Event Definition

- An AE is any untoward medical occurrence associated with the use of a drug in humans, whether or not it is considered drug-related.
- An AE can therefore be any unfavorable or unintended sign (including an abnormal laboratory finding), symptom, or disease (new or exacerbated) temporally associated with the use of study cream.

Additional Guidance for Events Meeting the Adverse Event Definition

- Any safety assessments (eg, ECG, vital signs measurements), including those that worsen from baseline, considered clinically significant in the medical and scientific judgment of the investigator (ie, not related to progression of underlying disease) are to be reported as an AE.
- Abnormal laboratory test results are to be reported as an AE if they are considered clinically meaningful, induce clinical signs or symptoms, require concomitant therapy, or require changes in study cream. Whenever possible, a diagnosis (eg, anemia, thrombocytopenia) should be recorded in the eCRF rather than the abnormal laboratory test result (eg, low hemoglobin, platelet count decreased).
- Exacerbation of a chronic or intermittent pre-existing condition/disease, including either an increase in the frequency and/or intensity of the condition, is to be reported as an AE.
- New conditions detected or diagnosed after the start of study cream application are to be reported as an AE.
- Signs, symptoms, or the clinical sequelae of a suspected drug-drug interaction are to be reported as an AE.
- Signs and/or symptoms from dosing errors of a study cream (eg, overdose) or a concomitant medication are to be reported as an AE.
- "Lack of efficacy," or "failure of expected pharmacological action" will not be reported as an AE or SAE. Such instances will be captured in the efficacy assessments. However, the signs, symptoms, and/or clinical sequelae resulting from lack of efficacy will be reported as an AE or SAE if they fulfill the definition of an AE or SAE.
- A condition that leads to a medical or surgical procedure (eg, endoscopy, appendectomy) will be reported as an AE if it occurs after obtaining informed consent/assent. If the condition is present before entering the study, then it should be captured as medical history.

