10.4. Statistical Analyses

10.4.1. Primary Analysis

A TEAE is any AE either reported for the first time or worsening of a pre-existing event after first application of study cream and up to 30 days after the last application of study cream. Analysis of AEs will be limited to TEAEs, but data listings will include all AEs regardless of their timing in relation to study cream application. Treatment-emergent AEs will be tabulated by the MedDRA preferred term and system organ class. Severity of AEs will be based on CTCAE v5.0 using Grades 1 through 5.

The subset of AEs considered by the investigator to have a relationship to study cream will be considered to be treatment-related AEs. If the investigator does not specify the relationship of the AE to study cream, then the AE will be considered treatment-related. The incidence of TEAEs, treatment-related TEAEs, serious TEAEs, Grade 3 or higher TEAEs, and TEAEs leading to

study cream interruption or study discontinuation will also be tabulated. A summary of primary endpoint analyses is provided in Table 12.

Table 12: Summary of Primary Endpoint Analyses

Endpoint	Population	Treatment	Population-Level Summary Metric
Incidence of TEAEs, treatment-related TEAEs, serious TEAEs, Grade 3 or higher TEAEs	FAS	Ruxolitinib 1.5% BID cream	Rate of TEAEs
Incidence of TEAEs leading to study cream interruption or study discontinuation	FAS	Ruxolitinib 1.5% BID cream	Rate of TEAEs
Incidence of TEAEs summarized by Grades of AE	FAS	Ruxolitinib 1.5% BID cream	Rates of TEAEs

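### Protocol Section 9.2 does not limit the elective or planned admission exclusion to pre-existing conditions, so a post-consent condition that meets only the hospitalization criterion may lose serious status

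*Protocol*

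**What the plan says.** Criterion (c) in Protocol Section 9.2 makes an event serious if it "Requires inpatient hospitalization or prolongation of existing hospitalization". Two exclusions follow.

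The first has no restriction of any kind: "Hospitalization for elective treatment or planned surgery (eg, stent replacement, hip surgery) is not considered an SAE".

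The second comes directly after it in the protocol, and it is restricted to admissions without an unfavorable occurrence: "Hospitalization for medical interventions in which no unfavorable medical occurrence occurred (ie, elective procedures or routine medical visits) is not considered an SAE".

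Section 9.1 uses the consent date to decide whether a condition is an adverse event at all. One that results in a procedure "will be reported as an AE if it occurs after obtaining informed consent/assent". A condition present before study entry is medical history. Section 9.3 uses the same dividing line for recording AEs and SAEs.

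Serious TEAEs are in the primary analysis. Section 10.4.1 tabulates "The incidence of TEAEs, treatment-related TEAEs, serious TEAEs, Grade 3 or higher TEAEs", and Table 12 repeats this for the FAS. SAP Section 9.2.2 counts participants with any serious TEAE, and Appendix A plans serious TEAE tables for the CT period, the LTS period and baseline to Week 52. The SAP has no seriousness definition of its own, so the protocol's definition governs.

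**The concern.** The consent-date line in Section 9.1 is not carried into the first exclusion in Section 9.2. As written, whether an admission makes an event serious can depend on whether the bed was booked ahead, rather than on whether the condition arose during the study.

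Two things are at stake. The first is the serious TEAE count in a study that the protocol describes as an FDA post-marketing requirement, with long-term safety data as its primary purpose (Section 2.2). The second is expedited reporting, because SAE status triggers the 24-hour rule in Section 9.4. With approximately 40 sites (Section 4.1) and about 100 participants, sites may also read the sentence differently.

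**Working it through.** **The plan's own figure.** Section 10.1 claims a greater than 99% chance of seeing at least one AE of interest at a 5% rate with 100 participants. 1 − 0.95^100 = 0.9941, so the claim reproduces. The present point does not affect it. What follows is mainly a question of wording.

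**Step 1: does the first exclusion do more than the second?** The second already covers elective procedures with no unfavorable occurrence. If the first meant only that, it would largely duplicate the second. Read as a rule in its own right, it reaches admissions in which an unfavorable occurrence did take place.

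**Step 2: is it needed for pre-existing conditions?** Section 9.2 opens by saying that an event that is not an AE cannot be an SAE. Under Section 9.1 a condition present before entry is medical history, and is an AE only if it worsens. A planned procedure for an unchanged pre-existing condition is therefore already outside the SAE definition. Literally applied, the first exclusion changes a classification only where there is an AE.

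**Step 3: one case, two admissions.** Take a condition that starts on cream, needs an overnight inpatient stay and meets no other seriousness criterion.

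- *Unplanned admission:* AE under 9.1; TEAE under 10.4.1; criterion (c) met; serious; 24-hour report.
- *Booked admission, literal reading:* AE under 9.1; TEAE under 10.4.1; excluded from (c); not serious; no 24-hour report.

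Only the scheduling differs.

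**Step 4: what stays intact.** In the second case the event remains in the overall TEAE, grade and relatedness tables. It is serious after all if it meets criterion (a), (b), (d), (e) or (f), or is a secondary malignancy. Complications are also protected: "If a complication prolongs hospitalization or fulfills any other serious criteria, the event is serious". The exposure is therefore limited to events for which hospitalization is the only criterion met.

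For the serious TEAE count, onset or worsening must also fall between first application and 30 days after the last. For SAE reporting, the period starts at consent.

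**Step 5: what one event is worth.** Inputs: n = 100 (Section 10.1) and exact (Clopper-Pearson) 95% limits.

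- 1/100: lower limit 1 − 0.975^(1/100) = 0.03%. The upper limit solves (1 − p)^100 + 100p(1 − p)^99 = 0.025, giving 5.45%.
- 0/100: lower limit 0; upper limit 1 − 0.025^(1/100) = 3.62%.

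The documents give neither a serious TEAE rate nor a share of booked admissions. As an illustration on assumed values only, let s be the true serious TEAE rate and f the share losing serious status. The chance of recording at least one is 1 − (1 − s(1 − f))^100:

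| s | f = 0 | f = 10% | f = 25% | f = 50% |
|---|---|---|---|---|
| 1% | 63.4% | 59.5% | 52.9% | 39.4% |
| 2% | 86.7% | 83.7% | 77.9% | 63.4% |

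The documents are equally compatible with f = 0.

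**The case against.** The best case for leaving the text alone has four parts.

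- **A narrower reading exists.** The sentence says that the hospitalization is not an SAE; it does not say that the underlying condition cannot be serious. Its examples suggest scheduled care for established disease, and planned could mean planned before the study. This is a fair reading, but the text does not settle it, and elective treatment carries no timing at all. An ambiguity in a seriousness definition is itself a reason to clarify it.
- **Other routes to serious status remain.** This stands, and it limits the point. The routes are not complete cover, however. The important-medical-event criterion is a matter of judgment. The default rule, "When in doubt as to whether hospitalization occurred or was necessary, the AE should be considered serious", helps only where occurrence or necessity is in doubt, and a booked admission need not raise that doubt.
- **The event is still analyzed.** This also stands. It is a TEAE if it falls in the window. If CTCAE does not classify it, the fallback scale in Section 9.3 names hospitalization under Grade 3, so it could appear among Grade 3 or higher TEAEs. The SAP's events of interest are summarized whether or not they are serious. None of this restores the serious TEAE count or the 24-hour report.
- **The case is rare, and site guidance may cover it.** Participants are 12 to 17 years old with mild to moderate disease, and the eCRF guidelines and SAE form guide are not available here. Both points argue for a small effect. Neither changes the protocol wording.

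A reader might infer that every scheduled admission for a condition arising on cream is left out of the serious TEAE endpoint. The documents do not support that: Section 9.1 keeps the event as an AE, and Section 9.2 leaves the other criteria open. Nor do they support any percentage-point figure for the undercount, since that would need a number of admissions that they do not give.

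**Conclusion.** The point holds in a limited form. The exclusion is a stated rule without the consent-date limit used in Sections 9.1 and 9.3. Read literally, it can remove serious status from a condition that began or worsened after consent, when a scheduled inpatient stay is the only criterion met.

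The direction is certain: an exclusion can only lower the serious TEAE count and suppress 24-hour reports. The size is not known and is probably small. One such event would change the reported result from 1/100 (95% CI 0.03% to 5.45%) to 0/100 (0% to 3.62%), and zero such events is quite possible. The conclusion assumes that sites apply the sentence as written and that no site guidance outside these documents narrows it. It is worth correcting because serious TEAEs are in the primary endpoint analyses and the correction is cheap.

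**What to change.** Reword the first exclusion in Section 9.2 to: *Hospitalization for elective treatment or surgery that was planned before informed consent, for a pre-existing condition that has not worsened since consent, is not considered an SAE.* Add that a scheduled inpatient admission for an AE that began or worsened after consent is assessed under criterion (c), in line with the consent-date rule in Section 9.1. The second exclusion can stay.

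Then check the AEs already recorded for any with a planned admission, and have seriousness reassessed under the clarified wording before the serious TEAE tables are produced.

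The cost is a sentence or two in an amendment or site clarification, a short data check, and possibly a few more SAE reports. No assessment, visit or analysis method changes.

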9.3. Recording and Follow-Up of Adverse Events and/or Serious Adverse Events

Adverse Event and Serious Adverse Event Recording

- An AE/SAE that begins or worsens after informed consent is signed should be recorded on the Adverse Events Form in the eCRF. All AEs/SAEs should be reported for enrolled participants, but only SAEs need to be reported for screen failure participants. For enrolled participants, conditions that were present at the time informed consent was given should be recorded on the Medical History Form in the eCRF. For detailed information, refer to the eCRF guidelines.
- When an AE/SAE occurs, it is the responsibility of the investigator to review all documentation (eg, hospital progress notes, laboratory reports, and diagnostic reports) related to the event.
- The investigator (or designee) will then record all relevant AE/SAE information in the eCRF.
- It is **not** acceptable for the investigator to send photocopies of the participant's medical records in lieu of completing the Adverse Events Form in the eCRF.
- There may be rare instances when copies of medical records for certain cases are requested. In this case, all participant identifiers, with the exception of the participant number, will be redacted by the site staff on the copies of the medical records before submission. These records can be submitted to Incyte Pharmacovigilance by email/fax per the contact information listed in the Study Reference Manual or as per SAE completing guidelines.
- The investigator will attempt to establish a diagnosis of the event based on signs, symptoms, and/or other clinical information. Whenever possible, the diagnosis (not the individual signs/symptoms) will be documented as the AE/SAE. When a clear diagnosis cannot be identified, each sign or symptom should be reported as a separate AE/SAE.

To the extent possible, each AE/SAE should be evaluated to determine the following:

- The severity grade (CTCAE v5.0 Grade 1 to 5). See below for further instructions on the assessment of intensity.
- Whether there is at least a reasonable possibility that the AE is related to the study cream: suspected (yes) or not suspected (no). See below for further instructions on the assessment of causality.
- The start and end dates, unless unresolved at the final safety follow-up visit.
- The action taken with regard to study cream as a result of the AE/SAE(s).
- The event outcome (eg, not recovered/not resolved, recovered/resolved, recovering/resolving, recovered/resolved with sequelae, fatal, unknown).
- The seriousness, as per the SAE definition provided in Section 9.2.
- The action taken with regard to the event. Note: If an AE is treated with a concomitant medication or nondrug therapy, this action should be recorded on the Adverse Events Form and the treatment should be specified on the appropriate eCRF (eg, Prior/Concomitant Medications, Procedures and Non-Drug Therapy).

Assessment of Intensity

The severity of AEs will be assessed using CTCAE v5.0 Grades 1 through 5. If an event is not classified by CTCAE, the severity of the AE will be graded according to the scale below to estimate the grade of severity.

The investigator will make an assessment of intensity for each AE and SAE reported during the study and assign it to 1 of the following categories:

- **Grade 1:** Mild; asymptomatic or mild symptoms; clinical or diagnostic observations only; treatment not indicated.
- **Grade 2:** Moderate; minimal, local, or noninvasive treatment indicated; limiting age-appropriate activities of daily living.
- **Grade 3:** Severe or medically significant but not immediately life-threatening; hospitalization or prolongation of hospitalization indicated; disabling; limiting self-care activities of daily living.
- Grade 4: Life-threatening consequences; urgent treatment indicated.
- Grade 5: Fatal.

Assessment of Causality

- The investigator is obligated to assess the relationship between study cream and each occurrence of each AE/SAE.
- A "reasonable possibility" of a relationship conveys that there are medical facts, evidence, and/or arguments to suggest a causal relationship, rather than that a relationship cannot be ruled out.
- The investigator will use clinical judgment to determine the possibility of a relationship.
- The investigator will also consult the RSI in the IB in making their assessment.
- Alternative causes, such as underlying or concurrent disease(s), concomitant therapy, and other risk factors, as well as the temporal relationship of the event to study cream application, will be considered and investigated.
- For each AE/SAE, the investigator **must** document in the medical notes that they have reviewed the AE/SAE and have provided an assessment of causality.
- With regard to assessing causality of SAEs:
 - There may be situations in which an SAE has occurred and the investigator has minimal information to include in the initial report. However, the causality assessment is one of the criteria used when determining regulatory reporting requirements. Therefore, it is very important that the investigator always make an assessment of causality based on the available information for every event before the initial transmission of the SAE.
 - The investigator may change their opinion of causality in light of follow-up information and submit the updated causality assessment.

Follow-Up of Adverse Events and Serious Adverse Events

- The investigator is obligated to perform or arrange for the conduct of supplemental measurements and/or evaluations as medically indicated or as requested by the sponsor to elucidate the nature and/or causality of the AE or SAE as fully as possible. This may include additional laboratory tests or investigations, histopathological examinations, or consultation with other health care professionals.
- Once an AE is detected, it should be followed in the Adverse Events Form in the eCRF until it has resolved or until it is judged to be permanent; assessment should be made at each visit (or more frequently if necessary) of any changes in severity, the suspected relationship to the study cream, the interventions required to treat the event, and the outcome.
- When the severity of an AE changes over time for a reporting period (eg, between visits), each change in severity will be reported as a separate AE.

- If a participant dies during participation in the study or during a recognized follow-up period, the investigator will provide the sponsor with a copy of any postmortem findings, including histopathology.
- Updated SAE information will be recorded in the originally completed eCRF and reported to Incyte Pharmacovigilance until resolution, stabilization, the event is otherwise explained, or the participant is lost to follow-up.
- Any updated SAE data (including SAEs being downgraded to nonserious) will be submitted to the sponsor (or designee) within 24 hours of receipt of the information.

9.4. Reporting of Serious Adverse Events

Regardless of suspected causality (eg, relationship to study cream or study procedure[s]), all SAEs occurring after the participant has signed the ICF/assent through the last safety visit or at least 30 days after the last application of study cream, whichever occurs later, must be reported to the sponsor (or designee) immediately, without undue delay but not later than within **24 hours** of obtaining knowledge of its occurrence unless otherwise specified by the Protocol. The investigator will submit any updated SAE data to the sponsor (or designee) immediately, without undue delay but not later than within 24 hours of it being available.

Investigators are not obligated to actively seek SAE information after conclusion of study participation (ie, after the safety follow-up visit or 30 days after the last application of study cream, whichever occurs later). If the investigator learns of any SAE, including death, at any time after a participant has been discharged from the study, and they consider the event to be reasonably related to the study cream or study participation, then the investigator must notify the sponsor (or designee) within 24 hours of becoming aware of the event.

After the initial AE/SAE report, the investigator is required to proactively follow each participant at subsequent visits/contacts. All SAEs will be followed until resolution, stabilization, the event is otherwise explained, or the participant is lost to follow-up (as defined in Section 7.3).

Prompt notification by the investigator to the sponsor regarding an SAE is essential so that legal obligations and ethical responsibilities toward the safety of participants and the safety of a study cream under clinical investigation are met.

If the SAE is not documented in the RSI of the IB for the study cream (new occurrence) and is thought to be related to the study cream, the sponsor or its designee may urgently require further information from the investigator for expedited reporting to health authorities. The sponsor or its designee may need to issue an Investigator Notification to inform all investigators involved in any study with the same drug that this SAE has been reported. Suspected unexpected serious adverse reactions will be collected and reported to the competent authorities and relevant ethics committees in accordance with Directive 2001/20/EC or as per national regulatory requirements in participating countries.

The sponsor has a legal responsibility to notify both the local regulatory authority and other regulatory agencies about the safety of a study cream under clinical investigation. The sponsor will comply with country-specific regulatory requirements relating to safety reporting to the regulatory authority, IRB/IEC, and investigators.

Investigator safety reports must be prepared for suspected unexpected serious adverse reactions according to local regulatory requirements and sponsor policy and forwarded to investigators as necessary.

An investigator who receives an investigator safety report describing an SAE or other specific safety information (eg, summary or listing of SAEs) from the sponsor will review and then file it along with the IB and will notify the IRB/IEC, if appropriate, according to local requirements.

Serious Adverse Event Reporting

- Information about all SAEs is collected and recorded on the Adverse Events Form in the eCRF.
- The investigator must report within 24 hours of learning of its occurrence any SAE via the EDC system (primary method) or by completing the Serious Adverse Event Report Form in English (only if the EDC system is not available). The contact information for Incyte Pharmacovigilance by email/fax is listed in the Study Reference Manual or as per the Incyte Reference Guide for Completing the Serious Adverse Event Report Form.
- In circumstances where the EDC system is not accessible for reporting SAE information (initial and/or follow-up SAE information) to the sponsor within 24 hours, refer to the Incyte Reference Guide for Completing the Serious Adverse Event Report Form. Once the EDC system is functional, the SAE report should be retrospectively added to the EDC system and follow-up should be completed through the EDC. The original copy of the Serious Adverse Event Report Form and the email or facsimile confirmation sheet must be kept at the study site (refer to the Incyte Reference Guide for Completing the Serious Adverse Event Report Form or Study Reference Manual for details and for the email address or fax number).
- Follow-up information is also recorded in the eCRF and transmitted to Incyte Pharmacovigilance via the EDC system. The follow-up report should include information that was not provided previously, such as the outcome of the event, treatment provided, action taken with study cream because of the SAE (eg, dose reduced, interrupted, or discontinued), or participant disposition (eg, continued or withdrew from study participation). Each recurrence, complication, or progression of the original event should be reported as follow-up to that event, regardless of when it occurs.

